13.1.1 Adverse Events overviews

The following overview tables will be generated by overall and study period (post-implant and post-ACT/DAPT at 3, 6, 9 and 12 months post-implant as defined in Section 5.4) further stratified by enrollment occurrence (before or at implant/after implant).

- Summary of the number and percentage of subjects with at least one
 - o SAE
 - SAE by procedure relatedness
 - SAE by device relatedness
 - Device related SAE by expectedness
 - SAE leading to study termination
 - SAE leading to study termination by procedure relatedness
 - SAE leading to study termination by device relatedness
 - Device related SAE leading to study termination by expectedness
 - SAE leading to death
 - SAE leading to death by procedure relatedness
 - SAE leading to death by device relatedness
 - Device related SAE leading to death by expectedness

The percentage denominator will be the number of subjects.

- Summary of the number and percentage of SAEs for:
 - SAE
 - SAE by procedure relatedness
 - SAE by device relatedness
 - Device related SAE by expectedness
 - SAE leading to study termination
 - SAE leading to study termination by procedure relatedness
 - SAE leading to study termination by device relatedness
 - Device related SAE leading to study termination by expectedness
 - SAEs leading to death
 - SAE leading to death by procedure relatedness
 - SAE leading to death by device relatedness
 - Device related SAE leading to death by expectedness

The percentage denominator will be the total number of SAEs.

13.1.2 Adverse Events Incidences

The incidence of SAE is defined as the number of subjects with occurrence of this SAE during the period of interest: post-implant and post-ACT/DAPT (at 3, 6, 9 and 12 months post-implant) as defined in Section 5.4.

The incidence rate of an SAE is defined as the number of subjects with occurrence of this SAE during the period of interest divided by the total number of subjects in the SAF during the period of interest.

COPYRIGHT LIVANOVA. ALL RIGHTS RESERVED. MAY NOT BE REPRODUCED WITHOUT PERMISSION. ALL HARD COPIES SHOULD BE CHECKED AGAINST THE CURRENT ELECTRONIC VERSION WITHIN MASTERCONTROL PRIOR TO USE AND DESTROYED PROMPTLY THEREAFTER. ALL HARD COPIES ARE CONSIDERED UNCONTROLLED DOCUMENTS.

The incidence, incidence rate, the number of events and the percentage of events (related to the total number of events) will be summarized by SAE general category and term, sorted alphabetically by overall and enrollment occurrence (further stratified by study period) for each of the following SAE categories and SAE subcategories:

Study: APR002 BELIEVE

- SAE
 - SAE by procedure relatedness
 - SAE by device relatedness
 - Device related SAE by Expectedness
- SAE leading to study termination
 - SAE leading to study termination by procedure relatedness
 - SAE leading to study termination by device relatedness
 - Device related SAE leading to study termination by expectedness
- SAE leading to death
 - SAE leading to death by procedure relatedness
 - SAE leading to death by device relatedness
 - Device related SAE leading to death by expectedness

Bar plots will be generated to show the incidence rates of overall SAE, SAE leading to study termination, SAE leading to death.

Incidence, incidence rate, the number of events and the percentage of events (related to the total number of events) will be summarized by SAE general category and term (sorted alphabetically) for SAEs only (overall and enrollment occurrence further stratified by study period) by the following SAE descriptors:

- SAE Criteria: in-patient hospitalization, prolonged hospitalization, permanent disability/incapacity, intervention to prevent life-threatening injury or permanent damage, life-threatening illness or injury.
- Action taken: treatment provided, aortic valve prosthesis re-intervention, pulse generator implanted, surgical intervention, non-surgical intervention, changes in medication regimen.

Linearized rate will be calculated, by overall and enrollment occurrence, as number of late (> 30 days) events, *e*, divided by late subject-years, *SY*, defined as the subject years accumulated in the period starting from the 31st day after implant. Linearized rate 90% CI will be calculated by means of the exact Poisson confidence limits as following:

90% CI lower limit =
$$\frac{\chi_{2e,0.05}^2}{2SY}$$

90% CI upper limit = $\frac{\chi_{2(e+1),0.95}^2}{2SY}$

where $\chi^2_{v,a}$ is the chi-square quantile for upper tail a probability on v degrees of freedom (Garwood 1936, Ulm 1990).

COPYRIGHT LIVANOVA. ALL RIGHTS RESERVED. MAY NOT BE REPRODUCED WITHOUT PERMISSION. ALL HARD COPIES SHOULD BE CHECKED AGAINST THE CURRENT ELECTRONIC VERSION WITHIN MASTERCONTROL PRIOR TO USE AND DESTROYED PROMPTLY THEREAFTER. ALL HARD COPIES ARE CONSIDERED UNCONTROLLED DOCUMENTS.

Plots will be generated to show the linearized rates, together with its 90% CI, of overall SAE, SAE leading to study termination, SAE leading to death.

Linearized rate, its 90% CI, will be summarized by SAE general category and term, sorted alphabetically by overall and enrollment occurrence, for each of the following SAE categories and subcategories:

- SAE
 - SAE by procedure relatedness
 - SAE by device relatedness
 - Device related SAE by expectedness
- SAE leading to study termination
 - SAE leading to study termination by procedure relatedness
 - SAE leading to study termination by device relatedness
 - Device related SAE leading to study termination by expectedness
- SAE leading to death
 - SAE leading to death by procedure relatedness
 - SAE leading to death by device relatedness
 - Device related SAE leading to death by expectedness

The following listings will be produced for all enrolled subjects:

- Deaths (the listing will present flags indicating the relevant study period);
- SAEs leading to study termination other than death;
- Unexpected device related SAEs.

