5.4 DEFINITIONS

Investigational Device (ID)	PERCEVAL (PMA P150011)
Baseline	Last non-missing observation (scheduled or unscheduled) before implant.
	Measurements collected the day of implant, in absence of other time information, are considered baseline data.
	If a subject is missing the planned baseline collection, the previous non-missing evaluation will become the baseline value.
	If any observation will be available before or on the day of implant, an unscheduled assessment done before the discharged visit can be used as baseline.
Study Day Count	The day of implant is defined as study Day 1.
	Calculate the study day according to the following rules:
	If date < study Day 1 then study day = Date – study Day 1
	If date ≥ study Day 1 then study day = Date – study Day 1 +1

LN-GLB-CLN-TEM-0033 rev1 Page 10 of 42

Study phases	
Pre-implant (Screening)	Screening and pre-implant assessments, where informed consent is signed and eligible criteria are met, before subjects will be considered enrolled in the study.
Implant (Enrollment)	During the implant until the establishment of a successful procedure.
Hospital Discharge	Before the subject is discharged or within 30 days of implant.
ACT/DAPT discontinua- tion visit	Visit required only for subjects on ACT/DAPT at hospital discharge: from 1 to 6 months (3 months preferred) postimplant.
Follow-up evaluations: First CT scan	Minimum of 30 days (+ 60 days) after discharge or discontinuation of ACT/DAPT (expected from 1 to 6 months post-implant).
Second CT scan	For subject with reduced leaflet motion previously detected by Core Lab; after the 1^{st} CT scan, but prior to 1 year follow-up visit (expected from 6 to 10 months post-implant).
1 year	Clinic visit at 1 year ± 1 month after the day of the implant.
Pre-implant period	Period from signing of the informed consent until the day before the implant.
Post-implant period	Period from successful implantation of Perceval bioprosthetic heart valve to 30-days after hospital discharge visit (for subjects discharged off ACT/DAPT) or ACT/DAPT discontinuation visit (for subjects discharged on ACT/DAPT).
Post-ACT/DAPT period	Period from 31 st day after the hospital discharge (for subjects discharged off ACT/DAPT) or 1 st day after the ACT/DAPT discontinuation (for subjects discharged on ACT/DAPT) to 1 year visit.

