13 SECONDARY SAFETY ANALYSIS

All safety data will be presented for the SAF and will be summarized descriptively by overall and, where specified, by occurrence of enrollment (subjects enrolled at implant/after implant) and/or study period (post-implant and post-ACT/DAPT).

Study: APR002 BELIEVE

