18.13 DATA DERIVATIONS

Derived variable	Derivation algorithm based on e-CRF version 8 dated 18 th July 2017
Concomitant	"Implant Surgical Details" e-CRF:
Procedures	Group "Implanted with a concomitant procedure" if CPYN= "Yes"
	Group "Implanted without a concomitant procedure" if CPYN= "No"
Subject symptoms	"Subject Clinical Assessment" e-CRF at "at 1 Month After ACT Dx (1st CT-Scan)" or "Reduced Leaflet Visit (2nd CT-Scan)" Visits:
	Group "Asymptomatic" if SCSYMPYN = "No"
	Group "Symptomatic" if SCSYMPYN = "Yes"
ACT/DATP	"Subject Clinical Assessment" and e-CRF:
	 Group "Subject on ACT/DAPT at hospital discharged (or 30-days after implant)" if SCDISCYN= "Yes"
	Group "Subject off ACT/DAPT at hospital discharged (or 30-days after implant" if SCDISCYN= "No"
Core Lab evaluation	"Vist (at 1 Month After ACT Dx or at Reduced Leaflet)" e-CRF:
by	Group "CT scan" if IMGTYPE= "4D CT Acquisition"
	Group "TEE" if IMGTYPE = "Transesophageal Echo"
Pre-implant period	If Enrolled Date= DXSTDAT2 ("Implant Surgical Details" e-CRF) then
	Start date: ICFDAT ("Inclusion/Exclusion Criteria" e-CRF)
	End date: DXSTDAT2 -1
	If Enrolled Date= ICFDAT then
	Start date=End date= "None".

LN-GLB-CLN-TEM-0033 rev1 Page 39 of 42

Post-implant period	If DXPER= "Yes" ("Implant Surgical Details" e-CRF) Start date: DXSTDAT2, End date: if SCDISCYN= "No" ("Subject Clinical Assessment" e-CRF) then End date= VISDAT (at Hospital Discharge visit) + 30 if SCDISCYN= "Yes" ("Subject Clinical Assessment" e-CRF) then End date= VISDAT (et ACT Disceptionation visit) + 30
Post-ACT/DAPT period	 End date= VISDAT (at ACT Discontinuation visit) + 30 Start date: if SCDISCYN= "No" ("Subject Clinical Assessment" e-CRF) then Start date= VISDAT (at Hospital Discharge visit) + 31 if SCDISCYN= "Yes" ("Subject Clinical Assessment" e-CRF) then Start date= VISDAT (at ACT Discontinuation visit) + 31 End date: VISDAT (at Year 1 visit)
Implant procedure completer	 DXPERF= "Yes" ("Implant Surgical Details" e-CRF) and DSSTDAT ≥ ACTDIDAT ("Study Termination" e-CRF) + 31 o if DSSTDAT missing, last available VISDAT ≥ ACTDIDAT + 31
Study completer	DSDECOD= "Completed" ("Study Termination" e-CRF)
SCR population	ICFDAT not missing ("Inclusion/Exclusion Criteria" e-CRF)
Enrolled Date	Derived from maximum between Consent Date and Implant Date. "Inclusion/Exclusion Criteria" e-CRF and "Implant Surgical Details" e-CRF Max(ICFDAT; DXSTDAT2)

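### SAEs by study period are crude percentages over periods of unequal length, and the linearized rate is not planned by period

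*SAP*

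**What the plan says.** SAP 13 plans descriptive safety tables overall and, where specified, "by occurrence of enrollment (subjects enrolled at implant/after implant) and/or study period (post-implant and post-ACT/DAPT").

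SAP 13.1.2 gives this definition of an SAE's incidence rate: "number of subjects with occurrence of this SAE during the period of interest divided by the total number of subjects in the SAF", with that denominator limited to the same period. The periods are "post-implant and post-ACT/DAPT (at 3, 6, 9 and 12 months post-implant) as defined in" SAP 5.4, and SAP 13.1.1 uses the same split. Neither section says whether the 3, 6, 9 and 12-month columns are cumulative or separate intervals.

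Under SAP 5.4 the post-implant period runs from implant to "30-days after hospital discharge visit (for subjects discharged off ACT/DAPT) or ACT/DAPT discontinuation visit (for subjects discharged on ACT/DAPT"), and the post-ACT/DAPT period follows until the 1-year visit. SAP 18.13 agrees for subjects discharged off therapy ("End date= VISDAT (at Hospital Discharge visit) + 30"). For subjects discharged on therapy it also adds 30 days to the discontinuation visit, so their post-ACT/DAPT period starts at that visit plus 31 days. Under 5.4 it starts on the first day after discontinuation.

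The person-time measure for SAEs is in SAP 13.1.2: "Linearized rate will be calculated, by overall and enrollment occurrence, as number of late (> 30 days) events", divided by subject-years from day 31. Study period is not among its strata.

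**The concern.** A percentage of subjects with at least one event grows with the length of the window in which events are counted. The denominator is limited to subjects in the period, which allows for attrition but not for how long each subject was observed. Two columns covering windows of different length can therefore differ when nothing about the risk has changed.

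The tables cover every SAE category, relatedness class and outcome, and the second period is named after the end of ACT/DAPT. Many readers will compare the columns and look for a change in risk. As planned, the columns cannot separate period length from early surgical risk or from a real change, and no by-period SAE rate is planned that could.

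**Working it through.** The documents state no SAE figure, so there is none to reproduce. The planned enrollment of about 88 does reproduce (75/0.85 = 88.2) and is used below for subject-years.

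**Inputs from the documents.** The discontinuation visit falls on day 30 to 180, with day 90 preferred (Protocol 7.10; SAP 18.6). Discontinuation is usually around 3 months (Protocol 7.5). The discharge visit is within 30 days of implant and the 1-year visit is nominally at day 365. Period boundaries are those of SAP 5.4 and 18.13.

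**Assumptions.** The SAE rate λ is constant at 0.1, 0.3 or 0.6 per subject-year and the same in both periods. There is no dropout, and days are counted from implant.

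**Formula.** P(at least one SAE in d days) = 1 − exp(−λd/365).

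For a day-90 stop at λ = 0.3 under 5.4: 1 − exp(−0.3 × 90/365) = 7.1% and 1 − exp(−0.3 × 275/365) = 20.2%. The other rows follow in the same way.

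| Stop, boundary rule | Days, post-implant v post-ACT/DAPT | λ = 0.1 | λ = 0.3 | λ = 0.6 |
|---|---|---|---|---|
| Day 90, SAP 5.4 | 90 v 275 | 2.4 v 7.3% | 7.1 v 20.2% | 13.8 v 36.4% |
| Day 90, SAP 18.13 | 120 v 245 | 3.2 v 6.5% | 9.4 v 18.2% | 17.9 v 33.2% |
| Day 180, SAP 5.4 | 180 v 185 | 4.8 v 4.9% | 13.8 v 14.1% | 25.6 v 26.2% |
| Day 180, SAP 18.13 | 210 v 155 | 5.6 v 4.2% | 15.9 v 12.0% | 29.2 v 22.5% |

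Over the whole post-ACT/DAPT period a day-90 stop gives about 2 to 3 times the post-implant percentage. A day-180 stop gives near equality or a reversal.

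**The 3, 6, 9 and 12-month cuts (day-90 stop, λ = 0.3).**
- Cumulative, SAP 5.4: about 0.1, 7.3, 14.0 and 20.2%, against 7.1% post-implant.
- Separate intervals, SAP 5.4: about 7.2% in each full 3-month interval against 7.1%, so almost no artefact. The 3-month column has almost no exposure (3 × 30.4375 − 90 = 1.3 days).
- Separate intervals, SAP 18.13: the 3-month column is empty. The 6-month column holds 6 × 30.4375 − 120 = 62.6 days, so 1 − exp(−0.3 × 62.6/365) = 5.0%. The 9 and 12-month columns give 7.2% each. The post-implant figure is 9.4%.

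**Person-time by period.** Take 88 subjects, a day-90 boundary and λ = 0.3. Post-implant there are 88 × 90/365 = 21.7 subject-years and 6.5 expected events. Post-ACT/DAPT there are 88 × 275/365 = 66.3 subject-years and 19.9 expected events. Both rates are 0.30, as they should be when the risk is constant.

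**The case against.** The strongest objection is to reading the two periods as on-therapy against off-therapy safety. A reader might infer that contrast from the name post-ACT/DAPT, but the definitions do not support it. A subject discharged off therapy also has a post-implant period, to 30 days after the discharge visit. With discharge on day 7 (assumed) the split is 37 against 328 days, or 3.0% against 23.6% at λ = 0.3. That large gap comes from a subject classed as off therapy at the start of both periods. Under 18.13 the post-implant period also takes in about 30 days after the discontinuation visit. This objection stands.

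A constant rate also fits poorly just after open-heart surgery. Protocol 2.3.1 reports more early than late stroke (1.2% v 0.8%) and major paravalvular leak (1.4% v 0.3%) in the pooled earlier studies, though not deaths (3.4% v 7.0%). At λ = 0.3 and a day-90 boundary under 5.4, an added early SAE probability of 1 − exp(−0.3 × (275 − 90)/365) = 14.1% would cancel the artefact. So the direction in the observed tables cannot be predicted. This stands too, and it shows that the percentages mix several influences.

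Third, time at risk is handled elsewhere. SAP 11.5 gives time-to-event analyses of the named valve safety events, with ACT/DAPT status at discharge as a Cox covariate, and SAP 5.2 gives Kaplan-Meier estimates with numbers at risk. That is true for those endpoints, but it does not supply exposure for the by-period SAE tables.

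Finally, the study is descriptive (Protocol 10), no test between periods is planned, and its purpose is the incidence of reduced leaflet motion. This limits what is at stake but does not make the columns comparable.

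**Conclusion.** The point holds as one about interpreting the by-period safety tables. The percentages take no account of period length and no by-period rate is planned. At the preferred 3-month stop, equal risk gives about 2 to 3 times the percentage over the whole post-ACT/DAPT period. That size rests on an assumed constant rate (0.1 to 0.6 per subject-year), no dropout, and reading the period as a whole or the cuts as cumulative. It is small for a day-90 stop under SAP 5.4 if the cuts are intervals, and it vanishes or reverses for stops near day 180.

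A reader might go further and infer that the tables will necessarily show more SAEs off therapy, or that they carry the comparison the study was set up to make. The documents support neither. The direction depends on the stop date, the boundary rule and early surgical risk, and no such comparison is an objective. The primary endpoint is unaffected.

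**What to change.** 1. Extend the linearized rate of SAP 13.1.2 to each study period, showing events, subject-years and the exact Poisson 90% CI. Show days 0-30 separately so that perioperative events do not dominate the post-implant rate.
2. State in 13.1.1 and 13.1.2 whether the 3, 6, 9 and 12-month columns are cumulative or separate intervals.
3. Reconcile SAP 5.4 with 18.13 on when the post-ACT/DAPT period starts for subjects discharged on therapy. Subject-years cannot be fixed until this is settled.
4. State which period holds subjects who never stop ACT/DAPT. Protocol 7.5 keeps them in the study to 1 year, but the period definitions do not cover them.
5. State where subject-years end for a subject without a 1-year visit, since 18.13 ends the period only at that visit.

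The rate method is already in the SAP and the dates are already collected, so no new data are needed. The cost is a few extra table columns and sparse counts in some cells. A footnote giving period lengths would warn the reader but would not provide a comparable figure.

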In 2010, the CAVALIER study was started. The study was designed to evaluate the safety and effectiveness of the Perceval valve with an extended indication in terms of subject age and preoperative mortality risk score. From February 2010, through September 2013, 658 subjects (mean age 78.3 years; 40% octogenarians; 64.4% females; mean STS score 7.2) underwent sutureless AVR in 25 European centers. The data of the CAVALIER study were used to obtain Perceval FDA approval. The study showed that the rates for all valve-related morbidity with the Perceval valve were less than two-times the OPCs, despite the advanced age, high STS scores, and the performance of concomitant cardiac procedures in this study population. There was no incidence of valve thrombosis or valve-related hemolysis reported in the study subjects. The hemodynamic performance of the Perceval valve was excellent with resultant salutary effects on the ventricular myocardium. Stable reduction of mean and peak pressure gradients was observed for all valve sizes. Corresponding to the observed reduction in gradients, subjects demonstrated an increase in the valve effective orifice area from preoperatively to discharge and remained stable through 3 years follow up. The assessment of functional status demonstrated marked and stable improvement in NYHA class for the majority of subjects throughout the study period.

The pooled results of the three studies were published by Shrestha et al. The three studies recruited a total of 756 subjects (mean age 78.5 years; 68.1% female) in 25 European sites. In the early period, the overall mortality rates were 3.4%; stroke events occurred in 1.2% of the subjects; major PVL occurred in 1.4%. Late events were reported as: all-cause mortality 7.0%, stroke 0.8% and major PVL 0.3%. No cases of valve thrombosis, SVD or valve migration were reported.

The safety and performance of the Perceval valve are also extensively documented in the scientific literature.

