10.2. SAMPLE SIZE

A sufficient number of subjects will be enrolled in this study to allow a minimum of 75 evaluable CT scans for the primary endpoint (evaluable scans are those where a determination of normal/abnormal leaflet motion is possible). Considering an attrition rate of 15% of subjects, the sample size targeted for enrollment is approximately 88 subjects.

A sample size of 75 evaluable CT scans produces an Exact two-sided 90% CI with a width lower than 13% when the sample proportion is lower than 10% (evaluation calculated using PASS software, version 13).

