5.1 GENERAL PRINCIPLES

The statistical analysis will be performed on the analysis study database with SAS version 9.4 or above (SAS Institute, Cary, N.C.).

If two or more of the analysis sets as defined in Section 6 coincide or the difference is less than 5%, presentations will only be prepared for the population less restrictive.

The default significant level will be 10%. Confidence Intervals (CIs) will be calculated at 90% confidence level and all tests will be two-sided, unless otherwise specified in the description of the analyses.

All the data collected and derived in the study will be presented in subject data listings.

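### The SAP's exact Poisson limits for linearized rates define the chi-square quantile by the wrong tail, so the limits cross for one or more events and the zero-event upper limit is 58 times too small

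*SAP*

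**What the plan says.** SAP section 13.1.2 defines the linearized rate as the number of late events e (more than 30 days after implant) divided by late subject-years SY, the latter "defined as the subject years accumulated in the period starting from the 31st day after implant". It continues: "Linearized rate 90% CI will be calculated by means of the exact Poisson confidence limits as following". Writing χ²(v, a) for the quantile with its two subscripts, the formulas are:

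- lower limit = χ²(2e, 0.05) / (2SY)
- upper limit = χ²(2(e+1), 0.95) / (2SY)

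The next line explains the symbol: it "is the chi-square quantile for upper tail a probability on v degrees of freedom". SAP section 5.1 sets the general convention: "Confidence Intervals (CIs) will be calculated at 90% confidence level and all tests will be two-sided".

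Protocol section 10.1.4 asks for linearized rates with 90% CIs but gives no formula. Nothing else in either document corrects the definition.

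**The concern.** The subscripts 0.05 and 0.95 are right for the exact interval only if they are lower-tail (cumulative) probabilities. The SAP says they are upper-tail probabilities, which exchanges the 5th and 95th percentiles while leaving the degrees of freedom where they were.

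The formula governs every linearized-rate interval in section 13.1.2. That covers all late SAEs by general category and term, by procedure and device relatedness, by expectedness, and by whether they led to study termination or death. Each is shown overall and by enrollment occurrence, and there are three plots.

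In a table that fine, some cells may hold no events. The protocol's own pooled experience with this valve, 756 subjects in section 2.3.1, says: "No cases of valve thrombosis, SVD or valve migration were reported". With no events, a literal reading gives a very small upper limit, and the table would appear to exclude almost any risk.

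**Working it through.** **Inputs**

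- Two-sided 90% level, so 0.05 in each tail (SAP sections 5.1 and 13.1.2).
- Degrees of freedom 2e and 2(e+1), subscripts 0.05 and 0.95, and the upper-tail definition (SAP section 13.1.2).
- Exposure, for illustration only: Protocol section 10.2 says "the sample size targeted for enrollment is approximately 88 subjects". The documents do not give SY. If all 88 are followed for exactly one year, late exposure is 88 × (365.25 − 30)/365.25 = 80.8 subject-years.

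**Step 1: the rule as written.** The value with upper-tail probability 0.05 is the 95th percentile, and the value with upper-tail probability 0.95 is the 5th percentile. Hence:

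- lower limit × SY = (95th percentile on 2e df) / 2
- upper limit × SY = (5th percentile on 2(e+1) df) / 2

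**Step 2: the exact limits.** The lower limit L solves P(X ≥ e | L) = 0.05 and the upper limit U solves P(X ≤ e | U) = 0.05, where X is Poisson. The solutions are:

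- L = (5th percentile on 2e df) / 2, taken as 0 when e = 0
- U = (95th percentile on 2(e+1) df) / 2

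Checked against the Poisson tails, each of these limits leaves 0.0500 (for e = 0, the upper limit only).

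**Step 3: results, as expected events (limit × SY)**

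| e | As written: lower | As written: upper | Exact: lower | Exact: upper |
|---|---|---|---|---|
| 0 | 0 (by convention) | 0.0513 | 0 | 2.9957 |
| 1 | 2.996 | 0.355 | 0.051 | 4.744 |
| 3 | 6.296 | 1.366 | 0.818 | 7.754 |
| 5 | 9.154 | 2.613 | 1.970 | 10.513 |
| 10 | 15.705 | 6.169 | 5.425 | 16.962 |

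The written lower limit exceeds the written upper limit for every e from 1 to 5,000. For e = 0 the ratio of exact to written upper limit is 2.9957 / 0.0513 = 58.4, whatever the exposure.

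**Step 4: zero-event upper limit as a rate, over assumed exposures**

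| Late subject-years (assumed) | As written, per 100 | Exact, per 100 |
|---|---|---|
| 60 | 0.085 | 4.99 |
| 68.8 (75 subjects, one year each) | 0.075 | 4.35 |
| 80.8 (88 subjects, one year each) | 0.064 | 3.71 |

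**Step 5: coverage.** "Sorted" means the two written limits are put in ascending order after calculation.

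| True mean count | As written | Sorted | Exact |
|---|---|---|---|
| 0.5 | 0% | 30% | 99% |
| 1 | 0% | 55% | 98% |
| 2 | 0% | 81% | 98% |
| 5 | 0% | 81% | 93% |
| 10 | 0% | 85% | 92% |
| 12 | 0% | 85% | 92% |

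On a grid of means from 0.5 to 12 in steps of 0.01, coverage is 0% as written, 30% to just under 90% sorted, and 90% to 99% for the exact interval. Sorting fails because 2e and 2(e+1) are then attached to the wrong ends: at e = 5 it gives 2.61 to 9.15, which is narrower than 1.97 to 10.51.

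**The case against.** The strongest reply is that the intent is plain and only one descriptive phrase is wrong. The SAP names the method, labels the limits, and prints the correct degrees of freedom and the correct cumulative levels. Putting the printed subscripts into a cumulative quantile function in SAS gives the right interval. That is true, and it is the likeliest outcome. But the programmer then gets the right answer by departing from the stated definition, and an independent validator who follows that definition would not reproduce it.

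For e ≥ 1 a literal implementation would expose itself, because the limits cross. That also stands. The silent case is e = 0, and harm there needs both a literal implementation and zero-event rows in the output. The SAP does not say that zero-event terms get rows, and section 18.8 replaces a wholly empty table with a statement that no subject qualifies.

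The reach is limited too. Valve thrombosis and structural valve deterioration are also analysed by time-to-event methods (SAP section 11.5), and counts and incidence rates are planned alongside. The primary endpoint uses exact binomial limits. None of these is affected.

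Finally, the 0% coverage is not universal. For true means of 0.01 to 0.05 expected events the written zero-event interval covers 95% to 99% of the time. The 0% figure applies to the range 0.5 to 12.

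**Conclusion.** The concern holds. As written, the rule does not give an exact 90% Poisson interval: the limits are inverted for every e ≥ 1 examined, and at e = 0 the upper limit is 58.4 times too small. These results follow from the SAP's own formula and definition and do not depend on exposure. Only the rates per 100 subject-years rest on the assumed follow-up.

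A wrong published interval would require someone to program the stated definition; the error most likely to pass unnoticed is the zero-event limit, if such rows are reported. The damage is confined to descriptive intervals for late SAE rates. The definition should nevertheless be corrected before any linearized rates are produced, because it is a plainly wrong rule in a safety analysis.

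**What to change.** In SAP section 13.1.2, keep the two formulas and change the definition of the second subscript from an upper-tail to a lower-tail (cumulative) probability. To remove doubt, add the SAS form:

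- lower limit = CINV(0.05, 2e) / (2SY), set to 0 when e = 0
- upper limit = CINV(0.95, 2(e+1)) / (2SY)

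The zero-event convention needs stating because a chi-square on 0 degrees of freedom is otherwise undefined in the program. Exchanging 0.05 and 0.95 in the formulas and keeping the upper-tail wording would be equivalent. Sorting the two results after calculation would not.

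The cost is one phrase and one added convention. Design, data collection, sample size and the primary analysis are unchanged.
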